#### **5.3.3 Serum drug levels**

The target range for everolimus serum levels in this study is between 5-10 mg/ml. For patients taking everolimus for 1 or 2 weeks, the only time an everolimus level will be assessed is on the morning of surgery from the reference laboratory. For those subjects taking everolimus for 3 weeks, a serum level will be obtained between days 10-12. All labwork will be performed at Tisch hospital, [name] or St Barnabas Medical Center [name] and the subjects taking everolimus for 3 weeks, the bloodwork will be done at the outpatient lab at Tisch Hospital as St Barnabas will only enroll controls

CONFIDENTIAL

This document and information is the property of the NYU School of Medicine and Langone Medical Center. Do not disclose or use except as authorized in writing by the study IND sponsor

---

#### **5.4 Method for Assigning Subjects to Treatment Groups**

All eligible patients will have TSC and FCD and will tentatively be scheduled or planning to have surgery. These eligible patients will be decided by [name], or [name]. [name], [name], [name] or [name] will also review their patient's charts to ensure they meet the inclusion criteria (review section 4.1 for all inclusion criteria). Once an eligible patient is decided upon, it will be presented to the patient if they would like to participate in this study. Anyone who declines at the NYU CEC will be asked to be take part in the control part of the study. Therefore it is up the patient to choose whether or not they will participate in the study and if they would like to be a part of the intervention or the control group.

The objective of this study is to show that everolimus can suppress mTOR signaling in patients. A control group is necessary for this study to compare the mTOR with patients who do not take the everolimus.

#### Subject Compliance Monitoring

Patients should be requested to bring their unused study drug and packaging to the clinic at each visit. Compliance should be verified by the investigator's staff through counting the number of tablets consumed between at the end of the study period.

#### **5.4 Prior and Concomitant Therapy**

Data will be collected on detailed information on all concomitant medical and over-the-counter medications taken by the patients. The dosage and time(s) of administration will be recorded at the start of the study and throughout the study period. For patients taking an EIAED or moderate CYP3A4 and/or PgP inhibitors, the dose of everolimus will be adjusted as specified in section 5-2.

CONFIDENTIAL

This document and information is the property of the NYU School of Medicine and Langone Medical Center. Do not disclose or use except as authorized in writing by the study IND sponsor

Patients are permitted to take their regular medications for epilepsy, including rescue medications (e.g., rectal Diastat, oral clonazepam) during the study period. Patients are also permitted to take medications for medical conditions that are not exclusionary (e.g., propranolol for migraine will be permitted but prednisone for systemic lupus erythematosus will NOT be allowed). Patients are not permitted to take immunosuppressive drugs (other than everolimus as a blinded medication) during the study period.

Patients will be asked to avoid drugs known to affect coagulation or platelet adhesion for 14 days before surgery.

### **5.5 Blinding of Study Drug**

*Not applicable.*

## **5.6 Receiving, Storage, Dispensing and Return**

### **5.6.1 Receipt of Drug Supplies**

Upon receipt of the study treatment supplies, an inventory must be performed and a drug receipt log filled out and signed by the person accepting the shipment. The designated study staff will count and verify that the shipment contains all the items noted in the shipment inventory. Any damaged or unusable study drug in a given shipment (active drug or comparator) will be documented in the study files. The investigator must notify study sponsor of any damaged or unusable study treatments that were supplied to the investigator's site.

### **5.6.2 Storage & Handling**

Study drug must be stored at 25°C (77°F); excursions permitted between 15°–30°C (59°–86°F); protect from light and moisture. Procedures for proper handling and disposal of anticancer drugs should be considered.

### **5.6.3 Dispensing of Study Drug**

After a subject with FCD or TSC is consented and entered into the study, they will be instructed on the dosage and administration times of the study medication. All subjects will receive a specific quantity of tablets and they will be asked to record the time that each dose is given. At each follow-up visit, they will be asked to bring back the medication that was not used so it can be reconciled with expected number of tablets to be used. This reconciliation will be logged on the drug reconciliation form, and signed and dated by the study team

### **5.6.4 Return or Destruction of Study Drug**

The site will maintain an overall drug accountability log for the study, as well as individual accountability records for each patient. The dose, amount dispensed, amount received, and amount remaining unused must be recorded in the source document. The patient will return all unused study drug at each dispensing visit and at the end of the study

At the completion of the study, there will be a final reconciliation of drug shipped, drug consumed, and drug remaining. This reconciliation will be logged on the drug reconciliation form, signed and dated. Any discrepancies noted will be investigated, resolved, and documented prior to return or destruction of unused study drug. Drug destroyed on site will be documented in the study files.

## **6 Study Procedures**

### **5.7 Visit 1 (Active/Control Patients)**

**NOTE:** This visit will occur within 6 weeks of Visit 2, which will be when patient will be entered into the study.

CONFIDENTIAL

This document and information is the property of the NYU School of Medicine and Langone Medical Center. Do not disclose or use except as authorized in writing by the study IND sponsor

After Informed Consent is obtained and study consent form is signed, Study Visit 1 will include the following, from interaction with the subject, and/or as applicable the subject's parents or guardian:

- A detailed review of the research subject's medical records and interview to ensure that the subject meets inclusion criteria and does NOT meet any of the exclusionary criteria.
- History of current seizure types and frequencies, concomitant medical or psychiatric disorders, and all prescribed and over-the-counter medications taken.
- Complete review of systems.
- Subject physical examination, including recording of vital signs, including height and weight to compute body mass index (BMI; see above) and body surface area (BSA), and neurological examination.
- Subject will be instructed to begin a daily seizure diary today that will be maintained and collected at the next visit.

**5.8 Visit 2 – (Active patients- 'NOTE: This visit will occur 7-21 days before surgery; patients/caretakers will be given Everolimus. )**

The following activities will be conducted and research subject information will be collected by interaction with the subject, and/or as applicable the subject's parents or guardian:

- Recent history will be reviewed for any change in their medical status or change in intake of prescribed or over-the-counter medication.
- Vital signs, physical and neurological examination.
- Collect and review seizure diary kept since Visit 1 and give new diary to be recorded until date of surgery. The protocol for study medication administration will be reviewed with the subject, and/or parent/guardian as applicable.
- Explanation of potential adverse events will be reviewed, as will the reporting of adverse events.
- Blood work: CBC and C-reactive protein (CRP). If not done prior to visit as part of PST (pre surgical testing)
- Review of the specific protocol for medication administration. (Active Patients Only at NYU CEC)
  - They will be instructed on the dosage and administration times of the study medication. All subjects will receive a specific quantity of tablets and they will be asked to record the time that each dose is given. They will be asked to bring back the medication that was not used so it can be reconciled with expected number of tablets to be used. This reconciliation will be logged on the drug reconciliation form, and signed and dated by the study team

6.2a Visit 2a – For patients taking the Everolimus for 3 weeks, at NYU CEC, they will have serum levels of everolimus drawn after 10-12 days on the medication. A trough level will be obtained. The study nurse or doctor will contact the patient with the results when available and will adjust the dose as described above. The nurse or doctor will also ask the patient to report any adverse events.

For active patients who reside outside of the NYC area and are unable to arrive at NYU CEC due to distance and travel issues prior to pre-admission testing, Visits 1 and 2 will be combined as one visit to be completed at least 7 days prior to Visit 3. For these patients with a combined Visit 1 and 2, this could mean a treatment window of 7-21 days depending both on which cohort they are in and how soon they can begin treatment.

Pre-surgical evaluation: Visit 2- Control Group

- Recent history will be reviewed for any change in medical status or change in intake of prescribed or over-the-counter medication.

CONFIDENTIAL

This document and information is the property of the NYU School of Medicine and Langone Medical Center. Do not disclose or use except as authorized in writing by the study IND sponsor

- Vital signs, physical and neurological examination
- A detailed seizure history during the prior week.
- Medication reconciliation.

Blood work: (pre surgical eval) CBC and C-reactive protein(CRP).

For control patients who reside outside of the NYC area and are unable to arrive at the study site due to distance and travel issues prior to pre-admission testing, Visits 1 and 2 will be combined as one visit and can be completed one day prior to Visit 3 if not earlier.

### **5.9 Visit 3 (Active/Control patients)– Day of Surgery NYU CEC**

The following activities will be conducted and research subject information will be collected:

#### Study drug dosing: (ACTIVE PATIENTS ONLY)

- On the day of surgery, the patient will take their last dose of everolimus with a 30 cc or less of water shortly after awakening and at least 3 hours before surgery
- A detailed seizure history during the prior week. A blood sample will be used for investigation per the IRB-approved protocol. This will include everolimus serum levels, systemic cytokines and mTOR activity levels. These samples will be batched and stored in -80 freezer until requested for analysis. )

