### **3.3 Secondary Outcome Measures**

- Other mTOR downstream/upstream markers in the brain (S6 phosphorylation) and peripheral VEGF-D levels.
- Blood and brain levels of cytokines (and TNF- $\alpha$ ) and inflammatory proteins (HMGB1) at the time of surgery
- Brain glutamate and GABA receptor expression at the time of surgery
- Blood levels of everolimus at the time of surgery
- **Electrocorticography** of minimum of 10 minutes. Site of expected maximal epileptogenicity will be recorded with grid or strip array of at least 12 contact points. **Extracellular field and recordings in acute ex-vivo brain slice:** After resection, one brain sample will be immediately placed, under sterile **conditions, into cold, oxygenated artificial cerebrospinal fluid (ACSF)**. Tissue will be transported to the lab and, within 5-10 min from resection, acute brain slices will be prepared. Extracellular field recordings, from visually identified neurons will be employed to assess overall cortical excitability, intrinsic neuronal firing properties and basic synaptic function.

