#### **5.11 Visit 5a (Active and concurrent comparison group) (if a second surgery is done at the end of invasive recordings) NYU Tisch Hospital**

Resected tissue at the time of surgery will be distributed by the Pathology Departments at the local institutions and samples will be used for investigation per the IRB-approved protocol. This tissue will be used for research analysis of biochemical, molecular, electrophysiological, and genetic measures.

6.5a Resected brain tissue will be distributed at the Pathology Department of the NYU Medical Center then stored in the Alexandria Center for Life Sciences, located at [name] on 9th floor a -80 freezer until requested to be analyzed..

The samples will be de identified and coded so that [name] will have access to the key. The samples will be stored and used only for analysis for this study. All tissue remaining after this study will be kept in our bank or destroyed per individual patient voluntary consent.

Samples will be stored secure labs in the above addresses. Our 3 NYU Pathologists-internal collaborators, [name], [name], and [name]) will perform analysis of brain resection specimens from patients on this study, and will be used for preparation of DNA/RNA assays. They will be looking for mutations in mTOR pathway genes. The samples will be studied using next gen sequencing, proteomics and/or Micro RNA assays, to search for mutations which may have caused the tuber or cortical dysplasia (CD). This analysis will focus on genes known to be involved in tuber/CD development including TSC1, TSC2, AKT1, AKT2, AKT3, MTOR, PTEN. Any variants that are found will be compared

CONFIDENTIAL

with those found in blood DNA samples from the same subjects. If subjects have indicated an interest in learning of the genetic findings, the findings will be provided to them. This information will be offered to the patients and their families through a physician or genetics counselor experienced with tuberous sclerosis. As this is not a clinical grade (CLIA-certified) analysis, the findings will be presented as research findings, which must be confirmed by a CLIA lab if any clinical action were considered based upon the information. The results of the genetic analysis will not be shared with anyone outside of the research team. The use of samples for this study is required.

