## **6 Statistical Plan**

### **6.1 Sample Size Determination**

#### **Statistical Methods**

Distributions of patient and disease characteristics will be summarized descriptively at study entry by dose duration cohort and across cohorts in the everolimus group and in the comparison group. Frequency distributions and cross tabulations will be presented for categorical variables. For continuous variables, summary statistics (means, medians, interquartile ranges, standard deviations, etc) will be provided along with graphical displays (e.g., boxplots) by treatment group.

Safety will be summarized within and across dose duration cohorts and compared with the events in the comparison group.

S6 phosphorylation levels in brain tissue sample at surgery will be summarized descriptively for each dose duration cohort and across cohorts in the treated group and in the comparison group. Further, levels will be compared between the treated and comparison group using 2 sample 2 sided t-tests (with appropriate transformations of levels if required to meet the assumptions of the method).

Similar analyses will be carried out for all additional continuous endpoints of interest. No adjustments for multiplicity will be made in this small study. Bivariate scatterplots and correlation coefficients will also be provided to examine the associations between the multiple endpoints.

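### The Visit 3 research blood draw is listed for active patients only, so blood cytokines and blood mTOR activity have no scheduled concurrent control value

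*Combined protocol and SAP*

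**What the plan says.** Section 5.9 is headed "Visit 3 (Active/Control patients)– Day of Surgery NYU CEC". Its first block, titled "Study drug dosing: (ACTIVE PATIENTS ONLY", holds the instruction on the last everolimus dose, followed by one bullet that combines a seizure history with the research blood sample. Of that sample the section says "This will include everolimus serum levels, systemic cytokines and mTOR activity levels". The next block, on procedures during surgery, is not restricted to one group and lists only electrocorticography and resected tissue.

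The control group's Visit 2 list gives "Blood work: (pre surgical eval) CBC and C-reactive protein(CRP". The active group's Visit 2 list (Section 5.8) gives "Blood work: CBC and C-reactive protein (CRP". Visit 1 (Section 5.7) lists no blood. The infection surveillance in Section 6.5 is again CBC and CRP.

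On endpoints, Section 3.3 includes an outcome beginning "Blood and brain levels of cytokines (and TNF", which also covers HMGB1, and a separate outcome for peripheral VEGF-D. On analysis, Section 6.1 specifies a two-sample t-test of treated against comparison subjects for S6, then states "Similar analyses will be carried out for all additional continuous endpoints of interest".

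Section 5.11 (Visit 5a), headed for both groups, says of tissue sequencing "Any variants that are found will be compared" and goes on to name blood DNA from the same people as the reference. It also describes lymphocyte mTOR proteins, serum HMGB1 and a serum volume per patient. Section 3.1 mentions a blood sample at surgery for everolimus and VEGF-D without naming a group.

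**The concern.** A site works from the visit list. If it does so here, treated patients give research blood on the day of surgery and controls give none. The two-group analysis in Section 6.1 would then have no second group for markers measured only in that sample.

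A cytokine level taken only from treated patients on the day of a craniotomy, with neither a baseline nor a concurrent control, cannot be attributed to everolimus. A day-of-surgery sample also cannot be collected later, so the loss is permanent for each control operated on under the present list.

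**Working it through.** No sample-size figure in the plan bears on this point, so the check is mainly a comparison of texts.

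**Step 1. Blood measures against scheduled draws**

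| Measure | Named in the Visit 3 active-only bullet? | Draw scheduled for controls? | Contrast the plan describes |
|---|---|---|---|
| Everolimus level | Yes | Not needed | Correlation with brain S6 (2.2) |
| Cytokines | Yes | No | Treated v comparison (6.1); historical controls for neuroinflammation (Study Summary, 2.2) |
| Blood mTOR activity | Yes | No | Treated v comparison (6.1) |
| HMGB1 | No; described in 5.11 | No | As for cytokines |
| VEGF-D | No; named in 3.1 | No | Before v after treatment (Study Summary, 2.2) |
| Blood DNA | No; described in 5.11 | No | Own tissue v own blood (5.11) |

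**Step 2. Size on the literal schedule.** Group sizes are 9 treated and 12 controls (Section 6.1 and Study Summary). The standard error of a difference in means is SD × √(1/n₁ + 1/n₀). With n₁ = 9 and n₀ = 0 it is undefined, so no concurrent comparison exists for cytokines or blood mTOR activity. The same holds for HMGB1 if it is assayed from that sample.

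**Step 3. What full sampling would give.** With n₁ = 9 and n₀ = 12, √(1/9 + 1/12) = 0.441. The normal approximation for 80% power at two-sided alpha 0.05 gives (1.960 + 0.842) × 0.441 = 1.24 SD. The exact noncentral-t calculation gives 1.30 SD. If some controls have already had surgery without a draw, the exact figure rises: 1.37 SD with 10 controls, 1.41 with 9, 1.46 with 8 and 1.52 with 7. Only large differences are detectable in any case, but a descriptive comparison is possible with controls and impossible without them.

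**Step 4. VEGF-D.** A before-and-after contrast needs a sample before the first dose. Active Visit 2 is when drug is handed out, and it lists only CBC and CRP. The after sample is described in Section 3.1; the before sample appears in no visit section.

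**Step 5. Blood DNA.** Section 5.11 covers both groups and uses each subject's own blood as reference, so controls need a blood sample for it. No visit section names a DNA draw for either group.

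**The case against.** The strongest reply is that this is a layout slip. The parent heading covers both groups, and the second bullet under the dosing title (seizure history and blood banking) is not about dosing. Section 3.1 restricts the surgical blood sample to no group, and Section 5.11 speaks of serum from each patient. The intention may well have been to bleed everyone.

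That is plausible, and it rules out the reading that the between-group analysis cannot be done or that the sponsor chose to leave controls out. It does not remove the contradiction. Neither Section 3.1 nor Section 5.11 gives a control draw time, and Visit 5a takes place only if there is a second operation. The seizure history is weak evidence of a slip, because controls have their own prior-week seizure history at Visit 2.

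Three further objections stand in part:

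- **VEGF-D.** A reader might infer that it is lost without controls. Its stated objective is within-patient, so the missing control draw does not defeat it.
- **Blood DNA.** A reader might infer that matched DNA is missing in 12/21 = 57% of subjects. That assumes treated patients' DNA comes from the Visit 3 tube, which the list does not say. DNA is also a within-subject reference, not a between-group endpoint.
- **Historical controls.** The Study Summary and Section 2.2 assign neuroinflammation to historical controls, so a concurrent comparison is not the only one contemplated. The documents describe no historical blood samples. Section 4.1.1 mentions banked tissue under another approved study, and whether that study also holds blood cannot be told from these documents.

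**Conclusion.** The visit schedule conflicts with the endpoint and analysis sections and should be corrected. Taken literally, it gives 9 treated values against 0 of 12 concurrent controls for blood cytokines and blood mTOR activity. The same applies to HMGB1 if it shares that sample, and controls have no scheduled blood DNA for the comparison in Section 5.11. VEGF-D has a different main gap: no pre-treatment draw is scheduled.

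These counts rest on two assumptions: that sites follow the visit list as written, and that all 9 treated patients reach surgery and are sampled. The finding about the text is firm; the sponsor's intention is not known. The effect is confined to secondary and exploratory measures. The primary S6 comparison uses brain tissue, and the safety analyses do not depend on this sample.

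**What to change.** 1. Move the research blood bullet in Section 5.9 out of the active-only block into a list for both groups.
2. Name the analytes by group: cytokines, HMGB1, lymphocyte mTOR proteins, VEGF-D and DNA in both; everolimus level in active patients only.
3. Use the same draw point on the day of surgery in both groups. Section 6.8.2 already puts the collection time on the tube label.
4. Add a pre-treatment VEGF-D tube to the active Visit 2 blood draw.
5. Reconcile the Study Summary and Section 2.2 with Section 6.1 by naming the comparator for each blood endpoint: concurrent control, historical control or own baseline.

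The cost is a short schedule amendment, a check that the control consent covers research blood, a few millilitres of blood from each control taken with routine surgical access, one extra tube from each active patient, and assays for up to 12 control samples and 9 baseline VEGF-D samples. The amendment cannot recover blood from controls who have already had surgery, so the number sampled should be reported for each marker.

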#### During surgery: (NYU Tisch Hospital)

- Intraoperative electrocorticography, performed in accordance with a standard protocol (see below).
- Resected tissue will be processed by the Pathology Departments at NYU Medical Center and a sample will be used for investigation per the IRB-approved protocol. This tissue will be used for primary analysis of biochemical, molecular, electrophysiological, and genetic measures.

